## 10.5 Appendix 5: Abbreviations

ABR	Annualized bleeding rate
ADA	Anti-drug antibodies
AE	Adverse event
ALT	Alanine aminotransferase
AST	Aspartate aminotransferase
AUC	Area under the curve
BDD	B-domain deleted
BU	Bethesda unit
CD4	Cluster of differentiation 4 (CD4 receptor)
COX	Cyclooxygenase
CRF	Case Report Form (either paper or electronic)
ED	Exposure day
e.g.	exempli gratia, for example
EHL	Extended half-life
EMA	European Medicines Agency
EPD	Electronic patient diary
EU	European Union
FDA	US Food and Drug Administration
FVIII	Human coagulation factor VIII
GCP	Good Clinical Practice
GMP	Good Manufacturing Practice
HIV	Human Immunodeficiency Virus
IB	Investigator's Brochure
ICF	Informed consent form
ICH	International Council for Harmonization
ie	Id est, that is
IEC	Independent Ethics Committee
IMP	Investigational medicinal product
IRB	Institutional Review Board
ITT	Intent to treat
IU	International units
IV	Intravenous
IxRS	Interactive voice/web response system
Kg	Kilogram
LoE	Loss of efficacy
LPLV	Last participant last visit
MedDRA	Medical Dictionary for Regulatory Affairs
NIMP	Non investigational medicinal product
PEG	Polyethylene glycol
PK	Pharmacokinetic
PMDA	Pharmaceuticals and Medical Devices Agency
PMI	Post-marketing investigation

PTP	Previously treated patients
QoL	Quality of Life
rFVIII	Recombinant factor VIII
SAP	Statistical analysis plan
SAE	Serious Adverse Event
SmPC	Summary of Product Characteristics
SoA	Schedule of activities
SUSAR	Suspected unexpected serious adverse reaction
$t_{1/2}$	Half-life
TEAE	Treatment-emergent adverse event
WHO	World Health Organization

# Statistical Analysis Plan

BAY 94-9027 / 19764

Page: 2 of 17

## Abbreviations

ABR	Annualized bleeding rate
AE	Adverse event
ATC	Anatomical Therapeutic Chemical Classification
CRF	Case report form
DSMB	Data safety monitoring board
ED	Exposure Day
EE	Energy expenditure
EMA	European Medicines Agency
ePD	Electronic patient diary
FDA	Food and Drug Administration
ITT	Intent to treat set
IU	International Unit
IV	Intravenous
LLOQ	Lower limit of quantification
MedDRA	Medical Dictionary for Regulatory Activities
mITT	Modified intent to treat set
MVPA	Moderate to vigorous physical activity
N/A	Not applicable
PA	Physical activity
PEG	Polyethylene glycol
PMDA	Pharmaceuticals and Medical Devices Agency
PMI	Post-marketing investigation
PT	Preferred term
PTP	Previously treated patient
rFVIII	Recombinant coagulation factor VIII
SAE	Serious adverse event
SAF	Safety analysis set
SAP	Statistical Analysis Plan
SOC	System organ class
TEAE	Treatment-emergent adverse event
WHO-DD	World Health Organization Drug Dictionary

## **1. Introduction**

Recombinant coagulation FVIII (rFVIII) is a replacement therapy in patients with Hemophilia A. Jivi (BAY 94-9027) has received marketing authorization amongst others from Food and Drug Administration (FDA), European Medicines Agency (EMA), Japanese Pharmaceuticals and Medical Devices Agency (PMDA), and Health Canada. The approved indication is: Treatment and prophylaxis of bleeding (including perioperative management) in previously treated patients (PTPs)  $\geq$  12 years of age with hemophilia A (congenital FVIII deficiency).

Regulatory requirements necessitate to assess the safety of Jivi in a total of 200 participants with 100 exposure days (ED) including pre-licensure participants of the development program from the studies 13024 (PROTECT VIII) and 15912 (PROTECT Kids). This study will include at least 25 participants for fulfillment of the requirements and provide a pooled analysis of all clinical studies (phase III/IV).

The purpose of this statistical analysis plan (SAP) is to describe the procedures and statistical methods to be used in analyzing and reporting results for the assessment of safety and efficacy of Jivi in Study 19764 and the integrated analysis of this study together with studies 13024 Part A (incl. extension) and 15912 (incl. extension).

### **Relevant documents**

- Clinical Study Protocol No. BAY 94-9027 / 19764 Version 2.0, dated 04 FEB 2020
- Integrated Clinical Study Protocol No. BAY 94-9027 / 13024, version 6.0, dated 20 JUN 2019
- Statistical Analysis Plan for study 13024, version 7.0, dated 11 SEP 2019
- Integrated Clinical Study Protocol BAY 94-9027 / 15912, version 5.0, dated 13 JUN 2017
- Statistical Analysis Plan for study 15912, version 3.0, dated 11 SEP 2019

## **2. Study Objectives**

The objective of the study is to confirm general safety and clinical efficacy with specific focus on immunogenicity and inhibitor documentation in a routine clinical use of the product in at least additional 25 participants during 100 ED in order to fully comply with Guideline requirements of 200 participants observed for at least 100 ED including participants from pre-authorization studies.

## Statistical Analysis Plan

BAY 94-9027 / 19764

Page: 5 of 17

**Table 2-1: Study objectives and endpoints for study 19764**

	Objectives	Endpoints throughout the study
Primary	

• To assess safety of Jivi

	
Primary Endpoint
 

• FVIII inhibitor development by the Nijmegen Bethesda assay

 
Secondary Endpoints
 

• Treatment-emergent adverse events (TEAE)

• Development of treatment-emergent anti-PEG antibodies

Secondary	

• To assess clinical efficacy of Jivi

	
Secondary Endpoint
 

• Annualized bleeding rate (ABR)

 
Other pre-specified
 

• Number of ED

• Percentage of participants with 0 bleeding events during a 6-month period

• Consumption

• Bleeding event attributes

• Incremental recovery

### 3. Study Design

The study will be a multicenter, single group, uncontrolled open label trial. Severe hemophilia A patients, age  $\geq 18$  years, will be enrolled and treated with prophylaxis treatment and for breakthrough bleeds for at least 100 ED, which may require 1-2 years depending on the prophylaxis regimen. Assessment of immunogenicity and safety will be performed at pre-defined ED as required by EMA FVIII Guideline.

The recommended starting dose is every 5 days treatment (45 IU/kg). An assessment of response to treatment will be performed at the next scheduled visit after 10-15 ED ( $\sim 8-10$  weeks). Subsequent dosing depends on need assessed by the investigator according to the following scheme and can be adjusted as needed.

## Statistical Analysis Plan

**BAY 94-9027 / 19764**

Page: 6 of 17

**Table 3-1: Recommended dose regimen**

Procedure	Duration	Dose regimen	Route of administration
Screening	> 2 weeks, ≤ 8 weeks	Continuation of previous treatment	
	Time to reach 10- 15 ED (~ 8 to 10 weeks)	Recommended starting dose 45 IU/kg every 5 days. Dose regimen can be adjusted any time in case of bleeds	IV injection
	Time to reach 100 ED	
0 bleeds during the first 8-10 weeks:
 
1 clinically relevant bleed during the first 8-10 weeks:
 
≥ 2 clinically relevant bleeds during the first 8-10 weeks:
	
Recommended dose regimen: 60 IU/kg every 7 days
 
Continue every 5 days at dose of 60 IU/kg
 
Or at investigator's judgement: Switch to 40 IU/kg 2x/week

Treatment Phase			IV injection

ED = exposure day, IV = intravenous

Clinically relevant: joint or muscle bleed that needs treatment

The total treatment duration is the time to reach 100 ED of Jivi. The total duration of study participation for each participant may require up to 2 years depending on the selected prophylactic regimen. When 25 participants have reached 100 ED, the study will be completed. Remaining participants may prematurely discontinue with reason 'Study terminated by sponsor' when a treatment duration of at least 6 months is reached.

## 4. General Statistical Considerations

### 4.1 General Principles

The study is not designed to test any predefined hypothesis. All analyses will be descriptive or exploratory.

The statistical evaluation will be performed by using the software package SAS release 9.2 or higher (SAS Institute Inc., Cary, NC, USA). All variables will be analyzed by descriptive statistical methods. The number of available and missing data, mean, standard deviation, minimum, quartiles, median, and maximum values will be calculated for metric data. Frequency tables will be generated for categorical data.

In addition to the analyses for study 19764, pooled results across the clinical phase 3/phase 4 studies will be presented. Therefore, data of study 19764 will be pooled with data from studies 13024 and 15912. CCR

Except when mentioned otherwise, all safety analyses will present results for study 19764 and pooled results of studies 19764, 13024 Part A (incl. Part A extension) and 15912 (incl.

extension). All safety analyses will be presented for the combined Jivi treatment group and will not distinguish between different regimens or treatment frequencies.

Efficacy analyses will be done for study 19764. If presented by treatment regimen, this will refer to the regimen at Visit 3. Participants who switch their regimen after Visit 3 will be assigned to a 'Variable frequency' group. Participants who dropped out before Visit 3 will be analyzed with their baseline regimen.

In addition to the study specific efficacy analysis, pooled results from studies 19764, 13024 Part A (incl. extension), and 15912 (incl. extension) for the main efficacy endpoint, i.e. annualized bleeding rates (ABR), will be provided.

Data handling rules described in this SAP refer specifically to study 19764. Data handling will be consistent with the data handling already applied to studies 13024 Part A and 15912. More details about the data handling of studies 13024 Part A and 15912 are available in the SAPs of these studies.

The following subgroup will be analyzed for safety and pooled efficacy:

- Age group 1: <12 years vs  $\geq$  12 years (at enrollment)

Subgroup tables will not be displayed by study/pool but by subgroup categories instead.

In case of multiple measurements before first treatment, the last one will be analyzed as baseline measurement.

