**Intervention Groups and Duration:**

All participants will be treated with three possible prophylactic regimens: 2x/week, every 5 days, or every 7 days with a recommended starting regimen of every 5 days. Participants are allowed to change the dose frequency during the study. All treatment decisions for identifying appropriate prophylactic treatment regimens should be guided by clinical judgement based on individual participant characteristics and treatment response.

The total treatment duration is the time to reach 100 exposure days (ED) of Jivi. The total duration of study participation for each participant may require up to 2 years depending on the selected prophylactic regimen. After the end of the study, the participants will be offered the option to participate in a non-interventional PASS study. While the decision for dose adjustment is at the investigator's discretion based on patient clinical characteristics, the following recommendations are provided: the starting dose is 45 IU/kg every 5 days.

Investigator may assess if dose regimen adjustment is warranted at the next planned visit (10-15 ED). A participant with zero bleed during the first 8-10 weeks of treatment may be considered for every 7 days at 60 IU/kg; a participant with 1 clinically relevant bleed during the first 8-10 weeks may be considered to either continue treatment every 5 days while at the 60 IU/kg or switch to twice weekly at 40 IU/kg; and a participant with  $\geq 2$  clinically relevant bleeds during the first 8-10 weeks should be changed to twice weekly at 40 IU/kg.

[figure not shown]
The details about duration and recommended dose regimen of study participation are as follows:

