### **Intervention Groups and Duration:**

Participants will be enrolled in the study and start the recommended starting treatment with every 5 days at a dose of 45 IU/kg. Participants with an increase in bleeding frequency may switch to a twice weekly regimen (2x/week, 40 IU/kg) at the investigator's discretion during the first 8-10 weeks.

At the next scheduled visit (after 10-15 ED, 8-10 weeks), all participants will have their bleeding frequencies reviewed by the investigator to determine any adjustment of the treatment. Participants who have no bleeds during the first 8-10 weeks are recommended to have the treatment with every 7 days at a dose of 60 IU/kg. Participants who have 1 clinically relevant bleed (e.g. joint or muscle bleed) during the first 8-10 weeks may continue the treatment with every 5 days at dose of 60 IU/kg; the regimen may also be adjusted to 2x/week (40 IU/kg) at the investigator's discretion after evaluation of bleed risk. If participants have  $\geq$  2 relevant bleeds during the first 8-10 weeks, these participants should change treatment to 40 IU/kg 2x/week. For overweight patients, the maximum total dose per injection should not be higher than approximately 6000 IU (rounded up to full vials).

Participants are allowed to change the dose frequency at any time during the study in case of increase in bleeding frequency. All treatment decisions for identifying appropriate prophylactic treatment regimens should be guided by clinical judgement based on individual participant characteristics and treatment response. It is recommended that the participant increases frequency (if treated every 7 days or every 5 days) after a second spontaneous bleed within a 3-month period.

The total treatment duration is the time to reach 100 (exposure days) ED of Jivi. The total duration of study participation for each participant may require up to 2 years depending on the selected prophylactic regimen. The details about duration and recommended dose regimen of study participation for each study periods are as follows:

Procedure	Duration	Dose regimen	Route of administration
Screening	> 2 weeks, ≤ 8 weeks	Continuation of previous treatment	
	Time to reach 10-15 ED (8 to 10 weeks)	Recommended starting dose 45 IU/kg every 5 days. Dose regimen can be adjusted any time in case of bleeds	IV injection
	0 bleed during the first 8-10 weeks:	Recommended dose regimen: 60 IU/kg every 7 days	

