### ABR:

$$\text{Annualized number of bleeds} = \frac{\# \text{ of bleeds} * 365.25 * 24 * 60}{\text{period}}$$

*Period* is defined as the number of minutes calculated from the date and time of the beginning of the evaluation period and the date and time of the end of the evaluation period.

Evaluation periods for study 19764:

- Main efficacy period: Time from injection at visit 3 to end of treatment
- Complete study: Time from first injection at visit 2 to end of treatment

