### **ABR:**

The ABR is the main efficacy endpoint of the secondary objective.

- ABRs will be presented for all bleeds, joint bleeds, spontaneous bleeds, , and trauma bleeds
- Results for the main efficacy period (Visit 3 to end of study) will be displayed by treatment regimen as described in section [4.1](#)
- Results for the complete study period (baseline to end of study) will be shown for the combined prophylaxis group

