### **Other efficacy endpoints**

Unless otherwise mentioned, results will be presented for complete study periods.

- Percentages of participants with 0 bleeds, 0 joint bleeds, 0 spontaneous bleeds, during the following treatment periods:
  - Last 6 months
  - Last year

- Treatment administration (overall, prophylaxis, treatment of bleeds): number of infusions (all and per year), consumption (IU, IU/kg, IU/kg/year, IU/kg/infusion, IU/year, IU/infusion)
- Reason for infusion
- Bleeding attributes: type, location, intensity, number of infusions to control, response to treatment
- FVIII levels pre- and post-infusion and incremental recovery: Results will be displayed by visit and overall (means per participant across visits)
- Pre- and post-infusion FVIII levels which are invalid for the calculation of recovery will be listed
- Bleeds into pre-existing target joints (annualized number, proportion of participants with 0 such bleeds) for the complete study period as well as the main efficacy period (starting with Visit 3)
- All untreated bleeds of study 19764 will be listed.
- Dosing regimens at baseline, Visit 3, and end of study will be compared in shift tables
- All dosing frequencies, planned doses, and reasons for dose modifications will be listed

[figure not shown]

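### The every-7-day bleeding-rate row leaves out anyone who switches after Visit 3, so it probably understates the rate of all who were on that regimen at Visit 3

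*SAP*

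**What the plan says.** SAP 4.1 sets the grouping for efficacy results: "If presented by treatment regimen, this will refer to the regimen at Visit 3". The next sentence makes an exception: "Participants who switch their regimen after Visit 3 will be assigned to a 'Variable frequency' group".

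SAP 6.2 applies this grouping to ABR: "Results for the main efficacy period (Visit 3 to end of study) will be displayed by treatment regimen as described in section" 4.1. SAP 4.5 defines the window: "Main efficacy period: Time from injection at visit 3 to end of treatment".

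The protocol says how participants reach and leave the every-7-day regimen:

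- **Entry** (Protocol 4.1): "Participants who have no bleeds during the first 8-10 weeks are recommended to have the treatment with every 7 days".
- **Exit** (Protocol 4.1): the recommendation is that "the participant increases frequency (if treated every 7 days or every 5 days) after a second spontaneous bleed within a 3-month period". The same section allows a change of frequency at any time if bleeding increases.
- **General permission** (Protocol 1.1): "Participants are allowed to change the dose frequency during the study".

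SAP 6.2 also plans this: "Dosing regimens at baseline, Visit 3, and end of study will be compared in shift tables". It adds a listing of dosing frequencies, planned doses and reasons for dose modifications.

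**The concern.** The two sentences in SAP 4.1 define different groups. The first defines a group fixed at the start of the main efficacy period. The second removes participants because of something that happens during that period, and the protocol's stated reason for that event is bleeding, which is the outcome being measured. Membership of the every-7-day row therefore depends partly on its own result.

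Because the SAP says the rows refer to the Visit 3 regimen, a reader may take the every-7-day figure as the bleeding rate of everyone given that regimen at Visit 3. The participants who bled most on it will tend to have been moved to another row. That row is not defined by regimen of origin, so the original group cannot be rebuilt from the summary rows.

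**Working it through.** The plan states no figure on this point, so there is nothing of its own to reproduce. The check has four parts.

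**1. When the row is too low.** Let p be the share of the Visit 3 every-7-day group who switch later, and M a mean ABR over the main efficacy period:

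M_all = (1 − p) × M_stay + p × M_switch

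The planned row shows M_stay. It lies below M_all whenever switchers bled more than stayers, and equals it when p = 0. Every 7 days is the least frequent of the three regimens, so any frequency change from it is upward, and bleeding is the trigger that Protocol 4.1 gives.

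One simulated case can be checked by hand. It assumes an underlying ABR of 2, 60% of bleeds spontaneous, gamma variation between participants, the recommendation always followed, and bleeding halved after a switch. Then p = 0.29, M_stay = 0.87 and M_switch = 3.42:

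0.71 × 0.87 + 0.29 × 3.42 = 0.618 + 0.992 = 1.61, and 0.87 / 1.61 = 0.54.

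**2. Range of sizes.** All bleed and switch rates are assumed. There were 48 scenarios per spontaneous rate, with 12,000 simulated participants each:

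- Between-participant variation: gamma shape 0.7, gamma shape 1.5, or one common rate.
- Switching at a second spontaneous bleed within 0.25 year: 50% or 100%.
- Bleeding rate after the switch: unchanged or halved.
- Trauma bleeds: 0.5 or 1 per year.
- Stopping at 6 months of treatment: 0% or 17% (5 of 30).

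Only participants with no bleed in the first 63 days enter the row, following the protocol's entry recommendation. After Visit 3, 87 exposure days remain, which at 7-day intervals is 87 × 7 = 609 days, or 609 / 365.25 = 1.67 years. Switchers move to twice weekly and reach 100 exposure days sooner.

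| Assumed spontaneous bleeds/year | Reclassified | M_stay / M_all | Mean lower by | Median unchanged |
|---|---|---|---|---|
| 0.5 | 3–10% | 0.78–0.97 | 3–22% | 47 of 48 |
| 1 | 8–25% | 0.63–0.93 | 7–37% | 29 of 48 |
| 2 | 13–62% | 0.48–0.92 | 8–52% | 10 of 48 |

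A second simulation took total ABR from 1 to 5 and applied no entry rule. With bleed-triggered switching and between-participant variation, the ratio was below 1 in every scenario (0.23–0.91).

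**3. What removes or reverses the effect.**

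- *Non-bleeders also move up* (16 scenarios per rate). If 25% of those with no spontaneous bleed in the first 6 months after Visit 3 move up, the ratios are 0.82–1.00, 0.67–0.97 and 0.52–0.95 at the three rates. If 50% do, they are 0.87–1.12, 0.73–1.07 and 0.56–1.08.
- *Switching unrelated to bleeding*: 1.00–1.06 in the second simulation.
- *One common high rate* of 5 per year, with half adherence or an 80% fall in bleeding after the switch: 1.10–1.14. This fits poorly with a group selected for having had no bleeds.
- *Nobody switches*: the row is unchanged. The chance of this is (1 − p)^n. At 0.5 per year, p is 0.033 to 0.096. For an assumed row of 10, 0.967^10 = 0.71 and 0.904^10 = 0.36. For 15, 0.967^15 = 0.60 and 0.904^15 = 0.22. The range is 22–71%.

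**4. Whether another planned output gives the missing number.**

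| Planned output | What it gives |
|---|---|
| 'Variable frequency' row | ABR of switchers from any Visit 3 regimen, mixed |
| Shift tables | Regimens at three time points, no ABR |
| Listing of frequencies and reasons | Individual dosing, no ABR |
| Combined ABR | Complete study, not split by regimen |
| Negative binomial analysis | Visit 3 regimen not mentioned |

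No visible planned table gives the main-period ABR by Visit 3 regimen with switchers retained.

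**The case against.** The strongest reply is that the row is not wrong. SAP 4.1 states the rule openly, SAP 6.2 refers back to it, and a separate 'Variable frequency' row signals that the other rows hold fixed-regimen participants. The number of switchers and their reasons can largely be recovered from the shift tables and the listing. No hypothesis is tested and no decision uses the row. The study exists mainly to supply safety data, and its 25–30 participants are spread over up to four rows.

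The size may also be modest. In the scenarios without early stopping at 0.5 spontaneous bleeds per year, the shift is 0.06–0.21 bleeds per year, against a standard error of 0.23–0.33 for an assumed 12-person row. At 1 per year it is 0.19–0.52 against 0.29–0.44. Only at 2 per year does it clearly exceed the noise (0.52–1.14 against 0.34–0.63). SAP section 7 mentions few treated bleeds, which points, weakly, to the lower rates. Finally, a row that keeps switchers includes time on other regimens, so it answers a different question and is not simply a correction.

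Most of this stands and limits the point: the size is not established, the endpoint is descriptive, and the existing rows are legitimate if labelled. But none of it supplies the ABR of the group that SAP 4.1 first names, and a planned table should not depend on readers noticing that its grouping is conditioned on the outcome.

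**Conclusion.** The point holds, with limited scope. The every-7-day row describes participants who stayed on that regimen. As the rate for everyone on it at Visit 3, its mean is likely too low, provided that switching is driven mainly by bleeding, as Protocol 4.1 describes. The direction is not guaranteed, because frequency changes are allowed generally. For every 5 days no direction is claimed, since participants there can move either way.

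The sizes rest entirely on assumed bleed and switch rates. They show what is possible and are not a forecast. The change is worth making because it is cheap and removes an outcome-dependent grouping, not because a study conclusion depends on it.

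**What to change.** In SAP 4.1 and 6.2:

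- Add a table of main-efficacy-period ABR by Visit 3 regimen with all later switchers retained in their Visit 3 group, and give the number of switches and the reasons per group.
- Keep the 'Variable frequency' split as a supplementary table, and label its fixed-regimen rows as participants who did not switch.
- State whether a dose change at an unchanged interval counts as a switch of regimen. SAP 4.1 does not say.

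No change to the clinical switching rule is proposed. The cost is SAP wording, one extra table and a label; the data are already collected. Two limits should be noted with the new table. The retained row includes some time on another regimen, so it is not a pure rate on every-7-day dosing. And regimens remain non-randomised, being chosen partly on bleeding before Visit 3, so the rows should not be compared as if they were treatment arms.

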### 9.2 Sample Size Determination

Descriptive statistics will be used. The sample size is defined by the Note for guidance on the clinical investigation of recombinant FVIII products in order to fulfill post-marketing requirements. During the clinical development program, a total of 232 participants were included in the Phase 1 and 2/3 clinical development program. Among these participants, 168 participants achieved >100 ED, and additional 17 participants achieved 50-100 ED. It is considered, that at least additional 25 participants would support the assessment of general safety and efficacy as required by guidelines EMA/CHMP/BPWP/144533/2009 rev.2 ([EMA 2017](#)).

A pooled analysis will be performed for all patients included in the Phase III and IV studies. The following trials will be included in the pooled analysis:

Study	Total number of participants included
PROTECT VIII	134
PROTECT Kids	73
Planned Phase IV study	≥25
Expected total	≥232

Assessment of safety will be done for the safety population including all participants with at least 1 injection of Jivi. Assessment of efficacy will be performed for the ITT population including participants with diary/injection data available.

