#### 10.4.3 Visit 3 – ED 10-15 (Week 8-10)

This visit should take place at least 72 hours after the last injection of Jivi.

- Dose regimen adjustment
- Blood sample collection **before** administration of study intervention:
  - Immunogenicity testing
  - Incremental recovery of Jivi
- In-hospital injection of Jivi
- Procedures and blood sample collection **after** administration of study intervention
  - Incremental recovery of Jivi (15-30 min after end of injection; see Section [8.1.2](#))
  - In case of any injection related AE at site, vital signs will be measured
- Concomitant medication review
- AE review
- Check of EPD entries and bleeding history
- Dispense study intervention for home injections in accordance with IxRS drug dispensing schedule

- Return used and unused study intervention
- Continue regular monthly contact between participant and the site to check EPD documentation and AE review until the End of Study/Early Termination

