### **4.2 Handling of Dropouts**

A participant who discontinues study participation prematurely for any reason is defined as a dropout if the participant has already been administered at least one dose of study drug.

The reasons for withdrawal will be listed in a table. Dropouts will be included in all safety analyses. They will also be included in efficacy analyses if the treatment duration is  $\geq 3$  months. The ABR will be calculated for these participants. It is assumed that a shorter treatment duration will not be sufficient to correctly estimate the ABR and would bias the results. When calculating ABRs, the end of the measuring period for a dropout is defined as the later of last available infusion record from the electronic patient diary (ePD) or the last procedure in a scheduled visit, excluding the final visit.

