#### Intent to treat set (ITT)

A participant will be included in the ITT if he received at least 1 infusion of study drug and has any injection/bleeding data available.

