#### Modified Intent-to-treat set (mITT)

A participant will be included in the mITT if he received at least 1 infusion of study drug and has injection/bleeding data for at least 3 months available.

A participant of study 13024 or study 15912 will only be included in the mITT if he entered the extension phase of the study.

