### Sensitivity analyses:

- Estimates and 95% confidence intervals from a negative binomial regression model will be presented for the ABRs of all bleeds, different lengths of evaluation periods will be addressed via an offset variable
- A subject listing including number and kind of bleeds and time in study will be provided for participants excluded from the mITT set

CCI

CCI

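### The SAP's rule for dropouts before Visit 3 affects no ABR when visits are on schedule, and no planned estimate tests whether leaving out early stoppers matters

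*SAP*

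**What the plan says.** **Regimen assignment.** SAP 4.1 shows by-regimen efficacy results according to the regimen at Visit 3. For those who never reach that visit it adds: "Participants who dropped out before Visit 3 will be analyzed with their baseline regimen".

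**Evaluation periods.** SAP 4.5 defines two. One is "Main efficacy period: Time from injection at visit 3 to end of treatment". The other runs from the first injection at Visit 2. Under SAP 6.2, the ABR is split by regimen only for the period that starts at Visit 3. The complete-study ABR is shown for all prophylaxis participants combined.

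**Analysis sets.** SAP 6.2 bases efficacy on the mITT unless it says otherwise. The mITT requires that a participant "has injection/bleeding data for at least 3 months available". SAP 4.2 applies the same floor to dropouts and gives its reason: "It is assumed that a shorter treatment duration will not be sufficient to correctly estimate the ABR and would bias the results". SAP 5.1 also defines an ITT set, which needs only one infusion and that the participant "has any injection/bleeding data available".

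**Sensitivity analyses.** SAP 6.2 plans a negative binomial model for all bleeds in which "different lengths of evaluation periods will be addressed via an offset variable". It also plans a listing of bleeds and time in study for participants outside the mITT.

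**Protocol.** Section 9.2 says: "Assessment of efficacy will be performed for the ITT population including participants with diary/injection data available". Sections 9.3 and 9.4.1 require at least 3 months for what they call the ITT population. The protocol's ITT in 9.3 is therefore the SAP's mITT, and the SAP's ITT is a wider set.

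**The concern.** The 4.1 sentence tells the reader that participants who leave before Visit 3 contribute to the efficacy results. For the ABR, the main efficacy endpoint, they do not.

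Exclusion may also depend on outcome. Protocol 2.3 and 8.3.7 describe hypersensitivity and loss of drug effect within the first 4 exposure days (ED). Section 2.3 describes discontinuation of Jivi in such cases, and 7.2 ends treatment and study participation together for anyone who withdraws. A participant for whom the product fails early could thus leave the bleeding-rate estimate because of that failure. With 25 to 30 treated participants, one or two such cases could be visible in the ABR. The listing would show them, but no planned estimate would show whether they matter.

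The 3-month floor answers a real problem: one person's bleeds over a few weeks, scaled to a year, make an unstable number. An offset model is the usual way to use unequal follow-up without that scaling, and the SAP already plans one. Because the model names no other set, it inherits the floor.

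**Working it through.** **1. Timing of Visit 3.** The protocol heading for the visit gives ED 10-15 and Week 8-10. On every-5-days dosing, ED k falls on day 1 + (k - 1) × 5.
- ED 10 = day 46 and ED 15 = day 71.
- Weeks 8 to 10 are days 56 to 70, inside that range, so the plan's own figure is reproduced.
- The Schedule of Activities allows ±14 days within the ED range. The latest nominal Visit 3 is day 70 + 14 = day 84.

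**2. Against the floor.** Three months is about 365.25 / 4 = 91 days.
- SAP 4.2 ends a dropout's period at the later of the last diary infusion or the last scheduled-visit procedure (final visit excluded). That gives at most about 84 days, below the floor.
- SAP 4.5 ends treatment 7 days after the last infusion, capped at end of study. The extreme is 84 + 7 = 91 days, which is borderline.
- If Visit 3 is late or missed and 3 months of data exist, the participant enters the complete-study ABR but still has no time in the by-regimen ABR.

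**3. Where a pre-Visit 3 dropout appears, visits on schedule.**

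| Output | Set or start | Included? |
|---|---|---|
| ABR by regimen | mITT, from Visit 3 injection | No |
| Complete-study ABR | mITT, from Visit 2 injection | No |
| Negative binomial model | mITT by default | No |
| SAP 6.2 listing | Outside mITT | Yes |
| Safety tables | Safety set | Yes |
| Withdrawal reasons | All dropouts | Yes |
| Any readable analysis on the SAP's ITT set | None found | n/a |

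**4. The floor suits individual rates.** Two bleeds in 56 days give 2 × 365.25 / 56 = 13.0 per year. Adding one such person to 25 participants with a mean ABR of 2 (an assumption) gives (25 × 2 + 13.0) / 26 = 2.42.

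**5. Effect on a model estimate.** The documents give no bleeding rate or early dropout rate, so these inputs are assumptions: 26 mITT participants followed 1.0 to 1.85 years, gamma-Poisson bleeds with shape 1, base ABR 2 or 4. Negative binomial results are the median change over simulated data sets (400 per scenario) when early stoppers are added.

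| Early stoppers | Base ABR 2 | Base ABR 4 |
|---|---|---|
| Two, 6 weeks, 3 bleeds each | +29% | +17% |
| One, 6 weeks, 3 bleeds | +13% | +8% |
| Two, 6 weeks, 1 bleed each | +6% | +3% |
| Two, day 16, 1 bleed each | +9% | +6% |
| Two, 6 weeks, no bleeds | -2% | -3% |
| Two, day 16, no bleeds | -1% | -1% |
| None | nil | nil |

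Day 16 is ED 4 on every-5-days dosing: 1 + 3 × 5 = 16.

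**6. Crude rate (total bleeds / total person-time), two stoppers at 6 weeks with 3 bleeds each.** Mean follow-up is (1.0 + 1.85) / 2 = 1.425 years, and 26 × 1.425 = 37.05 person-years. The stoppers add 6 bleeds and 2 × 42 / 365.25 = 0.23 person-years, 37.28 in total.
- Base 2: (74.1 + 6) / 37.28 = 2.15, or +7%. The simulated median is about +8%.
- Base 4: (148.2 + 6) / 37.28 = 4.14, or +3%.
- Base 2 with no bleeds: 74.1 / 37.28 = 1.99, or -1%.

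The negative binomial estimate moves more than the crude rate because its likelihood gives short, high-count records more weight than their share of person-time.

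**The case against.** **The exclusion is deliberate and disclosed.** This stands. The floor is in Protocol 9.3 and 9.4.1 and in SAP 4.2, 5.1 and 6.2, with a reason, and the excluded participants' bleeds are listed. It is not a hidden exclusion.

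**Early failures are captured elsewhere.** This stands. A reader might infer that they are only listed, but the documents do not support that beyond bleeding rates. Hypersensitivity and loss of efficacy are events of special interest (Protocol 8.3.7). SAP 6.4 tabulates those events, discontinuations, inhibitors and antibodies on the safety set, and safety is the primary objective.

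**The rule is not wholly dead.** A reader might infer that such participants can never enter any ABR. That follows from visit timing, not from a rule: a late or missed Visit 3 with 3 months of data still counts in the complete-study ABR. SAP 6.4 anticipates COVID-19 disruptions.

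**There may be few or no cases.** Also fair. Protocol 2.3 places the early immune response primarily in children under 6. This trial enrols adults with at least 150 prior ED and expects at least 25 of 25 to 30 to complete.

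**The offset model is itself sensitive to short exposure.** This stands in part. In the most unfavourable scenario above, most of the +29% reflects how the model weights short records, since the crude rate moves only about +8%. The direction is not fixed either: stoppers without bleeds lower the rate slightly. This is a reason to show the crude rate alongside, not to omit the check.

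**The endpoint is secondary and descriptive.** True, and it limits the weight of the point. It does not explain a sentence without effect or a defined set without use.

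**Conclusion.** The point holds in a limited form. With on-schedule visits, the 4.1 sentence on dropouts before Visit 3 affects no ABR. The SAP's ITT set is used by no readable analysis, and the one planned model built for unequal follow-up inherits a floor justified for individual rates. Exclusion that may depend on early failure is therefore not tested in any estimate.

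On the assumed inputs, including one or two early stoppers moves the negative binomial ABR by about -3% to +29% and the crude rate by about -1% to +8%. If nobody stops early, the change is nil. The documents support neither a claim that the reported ABR will be biased nor a claim that early failures go unreported. This is an inexpensive improvement to a descriptive secondary analysis and does not touch the primary safety objective.

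**What to change.** 1. **SAP 6.2.** Also run the planned negative binomial model on the SAP's ITT set over the complete study period, from the Visit 2 injection to end of treatment, beside the mITT estimate. Show the crude rate (total bleeds / total person-time) for both sets.
2. **SAP 6.2.** Keep the mITT for summaries of individual ABRs.
3. **SAP 4.1.** Delete the sentence on dropouts before Visit 3, or tie it to a named analysis where it can apply.
4. **SAP 4.2 and 4.5.** Reconcile the two end-of-period rules for dropouts, since they decide borderline 3-month cases.
5. **Protocol 9.2.** Align with 9.3 and 9.4.1, and state that the protocol's ITT corresponds to the SAP's mITT.

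The cost is wording changes, one further run of an already planned model and a simple rate. The mITT summaries stay as they are. The added estimate may differ slightly from the mITT result in either direction.
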